A cluster randomized controlled trial to evaluate the effect of placing Truenat platform/TB assays at primary health care clinics combined with rapid communication of results on time to treatment initiation of microbiologically confirmed TB. In a setup period (survey of study centers) before randomization, the healthcare facilities (=clinics) of 4 sites will be asked to provide information about the number of TB notifications per quarter covering the period 1/2018-6/2020. From this information the foreseeable number of examined patients ("size of a clinic") will be derived, which will be used as a strata variable in randomization process.

Facilities will be randomly allocated to the standard of care (control), or Truenat platform/TB assays. A cluster refers to a

	EDCTP
	clinic. The clusters will be assigned to intervention or control arm to one of two diagnostic procedures (SOC [smear microscopy and/or Xpert MTB/RIF Ultra off-site] vs Truenat platform/TB assays on-site) following a restricted randomization strategy, whereby 6 to 8 strata of clusters will be established using the stratification variables site (clinics belong to a site) and size and apply balance criteria for them. The number of strata per site depends on heterogeneity of the sizes of the clinics as established in setup period and may be increased, typically 1 or 2 strata per site will be established. The primary endpoint will be compared in an individual level analysis with strata and intervention as fixed effects and cluster as random effect.
Population	A total of 29 clinics will be randomized at the four participating sites aiming to enrol up to 150 adults (≥ 18 years of age) each (total approximately 4200) with signs and symptoms suggestive of TB. The number of clinics might be extended up to 37 due to the information gained in the setup period. Dependent on the loss to follow-up at 7 days, recruitment may need to be extended.
Inclusion/Exclusion Criteria (Site)	Based on information gained in the setup period sites will be included in the randomization process using the following criteria: Inclusion Criteria: Provision of TB treatment at the clinic Availability of electricity Willingness to participate Exclusion criteria: Patients with TB referred for treatment to other sites Sites with less than 10 patients registered for TB treatment per quarter

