For the purpose of sample size estimation, a matched design is regarded which is known to have a similar power in the range of number of clusters per treatment arm similar to this study (~15) since in that range the effects of gain of precision on one hand and the loss in degrees of freedom on the other hand are similar.

Applying an alpha-level of 0.05, a power of 80%, 12% prevalence, LTFU-rates of 10% (diagn., control), 10% (pretreatment intervention), 20% (pretreatment control), a cluster size of 150 and a within-pair

	coefficient of variation (default value 0.25 acc. Hayes & Bennett	
	1999), 13 clusters per study arm result (3900 patients). In order to	
	address uncertainty, 1 additional cluster pe	r treatment arm will be
	introduced, thus 14 cluster-pairs (28 clinics	, 4200 patients) result. If
	the information collected in the setup phas	e indicates that some
	clusters will be unable to enroll 150 patient	s during the study period
	the number of cluster may be increased up	to 36
Study Timeline	Period for ethics clearance	Q4 2021- Q2 2022
	Setup period	Q4 2021 - Q2 2022
	Import permits and importation	Q1 2021 -Q3 2022
	Kick off / training meeting	Q3 2022
	Training of sites on study procedures	Q2 2022
	Training of staff on Truenat procedures	Q2 2022
	First participant enrolled Q3 2022	
	Last participant enrolled Q3 2023	
	Complete follow-up	Q4 2023
	Data cleaning:	Q4 2023
	Data analysis: Q1 2024	
	Final report:	Q1 2024
	Total duration of study:	31 months

Protocol Version: 4.0 - CONFIDENTIAL - Page 20 of 57

3. Study schedule of events

Visit	Visit 1 (V1-D1)	Visit 2 (V2-D7)	Visit 3 (V3-D60)
Timeframe	Day 1	Day 7 (Week 1)	Day 60 (Month 2)
Procedure	<48h	Day 8 up to day 21	Day 61 up to day 90
Informed consent	x		
Eligibility assessment	x		
Enrolment (study register)	x		
Contact information (locator form)	x	(update)	
Baseline questionnaire (CRF-V1-D1)	x		
Baseline questionnaire with detailed socioeconomic questions (CRF-V1-D1-SE)	(x)		
Investigational product testing	(x)		
Follow-up questionnaire day 7 (CRF-V2-D7) – administered by telephone (3 attempts) if unsuccessful conduct home visit or call patient-nominated contact person		x	
Follow-up questionnaire day 60 (CRF-V3-D60) - administered by telephone (3 attempts) if unsuccessful conduct home visit or call patient-nominated contact person			x

Throughout follow-up data from the TB register and health facilities will be collected (study TB outcome worksheet)

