13.8 Sample size determination

For the purpose of sample size estimation, a matched design is regarded which is known to have a similar power in the range of number of clusters per treatment arm similar to this study (~15, 30). Sample size calculation were based on 972 scenarios using assumptions for

- TB prevalence: 12%, 16%, 20%
- Sensitivity for intervention group: 89%
- Sensitivity for control group: 70%, 75%, 80%
- Diagnostic LTFU intervention arm: 2%
- Diagnostic LTFU control arm: 5%, 10%
- Pre-treatment LTFU¹ intervention arm: 8%, 10%, 12%
- Pre-treatment LTFU control arm: 16%, 20%, 24%³¹
- Cluster size CS 100, 125, 150, 200 (cluster sizes are regarded as average values of a distribution of cluster sizes).
- Within pair coefficient variation \mathcal{CV}_m : 0.25 according to recommendation in case of missing information given in
- Alpha-level α = 0.05
- Power: 80% (β = 0.2)

From the prevalence, sensitivity and LTFUs in the diagnostics the proportions p of treated patients is derived ($p = prev \cdot sens \cdot (1 - LTFU_{diag}) \cdot (1 - LTFU_{pre - ther})$ for each of intervention and control arm ($\rightarrow p_i, p_c$).

The number of cluster pairs N_{cp} is calculated according to the following formula [Hayes RJ, Moulton LH 2017]:

$$N_{cp} = A + \left(z_{\alpha/2} + z_{\beta}\right)^{2} \frac{p_{i}(1 - p_{i})/CS + p_{c}(1 - p_{c})/CS + CV_{m}^{2}({p_{i}}^{2} + {p_{c}}^{2})}{(p_{i} - p_{c})^{2}}$$

whereby the result is rounded up to the next whole number, with A = 1 [Hayes RJ, Moulton 2017]²⁹. Note that Software PASS [PASS 2020] uses A=2, [Hayes and Bennett 1999]³⁰ uses A=0. z = quantile of normal distribution.

col Version: 4.0 - CONFIDENTIAL - Page 44 of 57

One should note that smaller cluster sizes (which would result in more clusters) are advantageous in terms of total number of patients to be recruited. Thus, the scenario has to be selected taking in into account number of patients on the one hand and efforts to recruit and organise sites on the other hand.

Following scenarios have been selected according to feasibility and mid-range choice of the ranges presented above:

Cluster size		Prevalence	Sensitivity control	diagn. LTFU control (diagn. LTFU for intervention: 0.02)	pre-trt. LTFU intervention	pre-trt. LTFU control	success proportion intervention	success proportion control	number of cluster pairs	Number of clusters	Number of patients
	100	16%	70%	10%	10%	20%	13%	8%	14	28	2800
	100	12%	70%	10%	8%	20%	10%	6%	15	30	3000

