- 5) A survival analysis will be performed on PP (i.e. participants without the protocol deviation) and in PPM population on time to treatment initiation to explore the possibility of bias.

Other measures can be taken depending on the distribution of the outcome related data

8 Sample size

For the purpose of sample size estimation, a matched design is considered which is known to have a similar power in the range of number of clusters per treatment arm similar to this study (~15). Sample size calculations were based on 972 scenarios using the following ranges of assumptions:

- TB prevalence: 12%, 16%, 20%
- Sensitivity for intervention group: 89%
- Sensitivity for control group: 70%, 75%, 80%
- Diagnostic LTFU intervention arm: 2%
- Diagnostic LTFU control arm: 5%, 10%

QMS Form number: FM-06-02-	CONFIDENTIAL	Page 19 of 26
05/v2.0		-

FIND >>>	Statistical Analysis Plan			
Protocol number:	TB041-3/1-TAN / -MOZ			
Document version:	5.0	Document date:	11-JUL-2023	

- Pre-treatment LTFU intervention arm: 8%, 10%, 12%
- Pre-treatment LTFU control arm: 16%, 20%, 24%¹
- Cluster size CS 100, 125, 150, 200 (cluster sizes are regarded as average values of a distribution of cluster sizes).
- Within pair coefficient variation CV_m: 0.25 according recommendation in case of missing information given in³²
- Alpha-level $\alpha = 0.05$
- Power: 80% ($\beta = 0.2$)

From the prevalence, sensitivity and LTFUs in the diagnostics the proportions p of treated patients is derived ($p = prev \cdot sens \cdot (1 - LTFU_{diag}) \cdot (1 - LTFU_{pre-ther})$ for each of intervention and control arm ($\rightarrow p_i, p_c$).

The number of cluster pairs N_{cp} is calculated according to the following formula [Hayes RJ, Moulton LH 2017]:

$$N_{cp} = A + (z_{\alpha/2} + z_{\beta})^{2} \frac{p_{i}(1 - p_{i})/CS + p_{c}(1 - p_{c})/CS + CV_{m}^{2}(p_{i}^{2} + p_{c}^{2})}{(p_{i} - p_{c})^{2}}$$

whereby the result is rounded up to the next whole number, with A=2, z= quantile of normal distribution.

The following scenarios have been selected according to feasibility and mid-range choice of the ranges presented above are shown in the tabulation below. Colours vary with cluster size and prevalence. The finally selected scenario is described below in red.

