Cluster size	Prevalence	Sensitivity control	diagn. LTFU control (diagn. LTFU for intervention: 0.02)		pre-trt. LTFU control	success proportion intervention	success proportion control	number of cluster pairs	Number of clusters	Number of patients
100	16%	70%	10%	10%	20%	13%	8%	14	28	2800
100	12%	70%	10%	8%	20%	10%	6%	15	30	3000
100	12%	70%	10%	10%	20%	9%	6%	17	34	3400
100	12%	70%	10%	12%	20%	9%	6%	18	36	3600
150	12%	70%	10%	10%	20%	9%	6%	13	26	3900

QMS Form number: FM-06-02-	CONFIDENTIAL	Page 20 of 26
05/v2.0		

FIND >>>	Statistical Analysis Plan				
Protocol number:	TB041-3/1-TAN / -MOZ				
Document version:	5.0	Document date:	11-JUL-2023		

150	16%	70%	5%	10%	20%	13%	9%	14	28	4200
150	16%	70%	10%	10%	20%	13%	8%	12	24	3600
200	12%	70%	10%	10%	20%	9%	6%	12	24	4800
200	16%	70%	5%	10%	20%	13%	9%	13	26	5200
200	16%	75%	10%	10%	20%	13%	9%	14	28	5600

Applying an alpha-level of 0.05, a power of 80%, 12% prevalence, diagnostic LTFU-rates of 10% (control), 10% (pre-treatment intervention), 20% (pre-treatment control), a cluster size of 150 and a within-pair coefficient of variation (default value 0.25), the results bring a total of 13 cluster pairs (3900 patients). In order to address uncertainty, 1 additional cluster pair will be added, bringing the total to 14 cluster-pairs (28 clinics, 4200 patients) to be included in the trial. If based on what will be observed in the initial setup period, smaller than average cluster sizes are expected, more sites will need to be included in the trial in order to match the total sample size.

Randomisation process

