3.0	4		The analysis strategy has been revised to include a GLMM with Poisson distribution to analyse the frequencies containing the absolute number of patients.	31-OCT-2022
3.0	8		Monitoring of enrolment by arm	31-OCT-2022

QMS Form number: FM-06-02-	CONFIDENTIAL	Page 24 of 26
05/v2.0		_

FIND >>>	Statistical Analysis Plan		
Protocol number:	TB041-3/1-TAN / -MOZ		
Document version:	5.0	Document date:	11-JUL-2023

Document version	Section reference	Change from	Change to	Document date
			throughout the study has been added to the strategies to minimize bias.	
3.0	Entire document		180 days follow-up has been removed from all outcomes and analyses.	31-OCT-2022
3.0	4		Analysis of missing data patterns has been revised to allow more flexibility and adapted plan in case of non-random missing data patterns	31-OCT-2022
3.0	4		P-value adjustment has been added	31-OCT-2022
3.0	2		The outcome related to the number of deaths has been removed since the cause of death independent of the disease cannot be distinguished from death due to TB.	31-OCT-2022
4.0	2		The wording of the outcomes has been revised to match the amended protocol.	03-APR-2023
4.0	4.2		Model parameters have been defined for the analysis of the primary outcome	17-MAY-2023
4.0	4.3		Model parameters have been defined for diagnosis and treatment related outcomes.	17-MAY-2023
			Analysis methodology has	

QMS Form number: FM-06-02-	CONFIDENTIAL	Page 25 of 26
05/v2.0		_

FIND >>>	Statistical Analysis Plan		
Protocol number:	TB041-3/1-TAN / -MOZ		
Document version:	5.0	Document date:	11-JUL-2023

Document version	Section reference	Change from	Change to	Document date
			been described for cost related endpoints.	
4.0	5		Items to be described are refined	17-MAY-2023
4.0	6		Subgroups are defined for the analysis	17-MAY-2023
4.0	4.3		Cost effectiveness analysis methodology was entered and revised	20-JUN-2023
4.0	3.2		MITT population defined	27-JUN-2023
4.0	4.1		The populations concerned by the analysis have been specified	27-JUN-2023
4.0	7		The description of the protocol deviation and related analysis methodology has been entered.	27-JUN-2023
5.0	2.1, 4.2		For the analysis of the count data, the wording "per month" has been removed.	11-JUL-2023

QMS Form number: FM-06-02-	CONFIDENTIAL	Page 26 of 26
05/v2.0		-

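### Does the constant A=2 in SAP section 8 undermine the sample size, when the table beside it comes from A=1?

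*SAP*

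**What the plan says.** SAP section 8 and protocol 13.8 share a formula: the number of pairs is a constant A plus a term built from the two success proportions, the cluster size and a within-pair coefficient of variation of 0.25. They differ in the constant.

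- SAP section 8: "whereby the result is rounded up to the next whole number, with A=2, z= quantile of normal distribution".
- Protocol 13.8: "whereby the result is rounded up to the next whole number, with A = 1", credited to the 2017 cluster-trial textbook. It adds "Note that Software PASS [PASS 2020] uses A=2" and notes that a 1999 paper uses A=0.

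Both documents then print the same ten scenarios with the same numbers of pairs. For the chosen scenario the SAP states "the results bring a total of 13 cluster pairs (3900 patients") and continues "In order to address uncertainty, 1 additional cluster pair will be added", which makes 14 pairs, 28 clinics and 4200 patients. The protocol synopsis agrees: "13 clusters per study arm result (3900 patients").

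Both sections also say that 972 scenarios were examined and that the ones shown were picked for feasibility and as mid-range choices.

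**The concern.** A reader who takes the SAP alone and puts its printed constant into its printed formula gets 14 pairs for the chosen scenario, not 13. On that reading the pair added for uncertainty is no reserve at all, because it is needed just to reach 80% power. Keeping a reserve would then take 15 pairs, that is 30 clinics and 4500 patients. If A=2 were the intended constant, every row of the table would be wrong and the trial would have less margin than it claims.

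Two neighbouring details add to the doubt. The listed values do not multiply to 972 scenarios. And nine of the ten scenarios shown, including the chosen one, use 70% control sensitivity. That is the lowest of the three listed values and the one that needs the fewest clusters, so mid-range does not describe it.

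**Working it through.** **Inputs for the chosen row** (SAP section 8; identical in protocol 13.8): prevalence 12%; sensitivity 89% intervention, 70% control; diagnostic LTFU 2% and 10%; pre-treatment LTFU 10% and 20%; cluster size 150; coefficient of variation 0.25; two-sided alpha 0.05; power 80%.

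**Success proportions**

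- p_i = 0.12 × 0.89 × 0.98 × 0.90 = 0.09420
- p_c = 0.12 × 0.70 × 0.90 × 0.80 = 0.06048

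**Term added to A**

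- (1.960 + 0.8416)² = 7.849
- Numerator: 0.09420 × 0.90580/150 + 0.06048 × 0.93952/150 + 0.0625 × (0.09420² + 0.06048²) = 0.000569 + 0.000379 + 0.000783 = 0.001731
- Denominator: (0.09420 − 0.06048)² = 0.001137
- 7.849 × 0.001731/0.001137 = 11.949 (from unrounded values)

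A=1 gives 12.949, rounded up to **13**, the stated figure. A=2 gives 13.949, rounded up to 14.

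**All ten rows**, in the table's order:

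| Row (cluster size, prevalence) | Term added to A | Printed | A=0 | A=1 | A=2 |
|---|---|---|---|---|---|
| 100, 16% | 12.551 | 14 | 13 | 14 | 15 |
| 100, 12%, pre-treatment LTFU 8% | 13.750 | 15 | 14 | 15 | 16 |
| 100, 12%, pre-treatment LTFU 10% | 15.221 | 17 | 16 | 17 | 18 |
| 100, 12%, pre-treatment LTFU 12% | 16.977 | 18 | 17 | 18 | 19 |
| 150, 12% (chosen) | 11.949 | 13 | 12 | 13 | 14 |
| 150, 16%, diagnostic LTFU 5% | 12.887 | 14 | 13 | 14 | 15 |
| 150, 16%, diagnostic LTFU 10% | 10.170 | 12 | 11 | 12 | 13 |
| 200, 12% | 10.314 | 12 | 11 | 12 | 13 |
| 200, 16%, diagnostic LTFU 5% | 11.389 | 13 | 12 | 13 | 14 |
| 200, 16%, control sensitivity 75% | 12.242 | 14 | 13 | 14 | 15 |

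A=1 matches ten of ten; A=0 and A=2 match none. Rounding cannot account for this, since the whole column shifts by exactly one.

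**Power for a given number of pairs n.** Inverting the formula, power = Φ(√((n − A)/V) − 1.960), with V = 0.001731/0.001137 = 1.522.

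| Pairs | A=1 | A=2 |
|---|---|---|
| 13 | √(12/1.522) − 1.960 = 0.848, so 80.2% | √(11/1.522) − 1.960 = 0.728, so 76.7% |
| 14 | √(13/1.522) − 1.960 = 0.962, so 83.2% | √(12/1.522) − 1.960 = 0.848, so 80.2% |

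A noncentral paired t calculation with 13 degrees of freedom gives 80.0% at 14 pairs, so the target is also met on that stricter basis.

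**Scenario count.** The listed values give 3 prevalences × 3 control sensitivities × 2 control diagnostic LTFU × 3 × 3 pre-treatment LTFU × 4 cluster sizes = 648, and 972/648 = 1.5. A third value for control diagnostic LTFU, the only factor with two values, would give 3 × 3 × 3 × 3 × 3 × 4 = 972 exactly. Six cluster sizes instead of four would too. None of the ten rows depends on the count.

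**Control sensitivity.** At 14 pairs with A=1 and the other chosen inputs unchanged:

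| Control sensitivity | 12% prevalence | 16% | 20% |
|---|---|---|---|
| 70% | 83.2% | 88.6% | 91.7% |
| 75% | 70.7% | 77.5% | 81.8% |
| 80% | 55.6% | 62.4% | 67.1% |

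The chosen row pairs the most favourable listed control sensitivity with the least favourable listed prevalence.

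**The case for a change.** The strongest case for a correction is that a sample-size section should be reproducible from its own printed formula, and this one is not. The constant also decides whether the 14th pair is a reserve (80.2% rising to 83.2%) or is needed to reach the target (76.7% rising to 80.2%), and changing it costs one character. All of that is true. It shows a misprint in the SAP, not a fault in the design, because protocol 13.8 gives the constant that was used, names the rival convention and its source, and prints the same results.

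That A=2 is a slip remains an inference. The ten-row match and the common textbook source carry it. The SAP change history adds little: its only section 8 entry is "Monitoring of enrolment by arm", but a constant present since the first issue would leave no entry whether or not it was intended. If the sponsor did intend A=2, the table and the 13-plus-1 sentence would be wrong instead, and 14 pairs would be the requirement. Even so, the planned number would still reach 80%.

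The sensitivity point has more substance, since power falls to 55.6% if control sensitivity is 80% at 12% prevalence. But 70% has a basis in the documents. The control arm mixes smear microscopy and off-site Xpert; the protocol's lay summary puts these at about 50% and 90%, and an even mix (an assumption) gives 70%. Protocol 5.3 and 5.4 describe smear as still the main tool in both countries, so a lower figure is also possible. At 60%, again an assumption, the same formula gives 96.7% power at 14 pairs with A=1. Control sensitivity is printed in every row, so nothing is hidden.

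**Conclusion.** The concern is factually right about the constant, but it calls for no change to the plan. It is a clerical discrepancy that the protocol resolves, and an analyst who rebuilds the table will settle on A=1 at once. Under A=1 the 13 pairs, the additional pair, 28 clinics, 4200 patients and 80% power are all correct. Under A=2 the planned 14 pairs still give 80.2%. The constant appears in no model, test or interval. The separate allowance for more clinics ("The number of clinics might be extended up to 37 due to the information gained in the setup period") responds to recruitment and clinic size, not to A.

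The side issues do not change this. Replacing 972 with 648 could introduce an error if a listed value was dropped, and only the sponsor knows how many scenarios were run. Describing the selection as mid-range is loose for control sensitivity, but the stated power is delivered under the stated inputs.

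These figures rest on the documents' matched-pair approximation, a default coefficient of variation of 0.25, an average cluster size of 150 and unrounded proportions. They are not power figures for the planned mixed model.

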3.0	4		The analysis strategy has been revised to include a GLMM with Poisson distribution to analyse the frequencies containing the absolute number of patients.	31-OCT-2022
3.0	8		Monitoring of enrolment by arm	31-OCT-2022

QMS Form number: FM-06-02-	CONFIDENTIAL	Page 24 of 26
05/v2.0		_

FIND >>>	Statistical Analysis Plan		
Protocol number:	TB041-3/1-TAN / -MOZ		
Document version:	5.0	Document date:	11-JUL-2023

Document version	Section reference	Change from	Change to	Document date
			throughout the study has been added to the strategies to minimize bias.	
3.0	Entire document		180 days follow-up has been removed from all outcomes and analyses.	31-OCT-2022
3.0	4		Analysis of missing data patterns has been revised to allow more flexibility and adapted plan in case of non-random missing data patterns	31-OCT-2022
3.0	4		P-value adjustment has been added	31-OCT-2022
3.0	2		The outcome related to the number of deaths has been removed since the cause of death independent of the disease cannot be distinguished from death due to TB.	31-OCT-2022
4.0	2		The wording of the outcomes has been revised to match the amended protocol.	03-APR-2023
4.0	4.2		Model parameters have been defined for the analysis of the primary outcome	17-MAY-2023
4.0	4.3		Model parameters have been defined for diagnosis and treatment related outcomes.	17-MAY-2023
			Analysis methodology has	

QMS Form number: FM-06-02-	CONFIDENTIAL	Page 25 of 26
05/v2.0		_

FIND >>>	Statistical Analysis Plan		
Protocol number:	TB041-3/1-TAN / -MOZ		
Document version:	5.0	Document date:	11-JUL-2023

Document version	Section reference	Change from	Change to	Document date
			been described for cost related endpoints.	
4.0	5		Items to be described are refined	17-MAY-2023
4.0	6		Subgroups are defined for the analysis	17-MAY-2023
4.0	4.3		Cost effectiveness analysis methodology was entered and revised	20-JUN-2023
4.0	3.2		MITT population defined	27-JUN-2023
4.0	4.1		The populations concerned by the analysis have been specified	27-JUN-2023
4.0	7		The description of the protocol deviation and related analysis methodology has been entered.	27-JUN-2023
5.0	2.1, 4.2		For the analysis of the count data, the wording "per month" has been removed.	11-JUL-2023

QMS Form number: FM-06-02-	CONFIDENTIAL	Page 26 of 26
05/v2.0		-
